7.1.1.2 Spleen Size Assessment by Physical Examination

Spleen size, assessed by physical examination as the distance below the LCM at the midclavicular line, will be performed with each scheduled physical examination.

7.1.1.3 Disease-Related Signs and Symptoms

Patient-reported disease-related symptoms as assessed by the validated PRO instrument MPN-SAF TSS 2.0 (Appendix 5) will be collected daily using an electronic diary and will be evaluated as a part of the dose–response relationship. Patients must begin reporting symptoms via electronic diary at least 7 days before starting pacritinib treatment and will continue until the Week 48 visit. After Week 48, the patient will fill out the questionnaire (Appendix 3) at each follow up visit. The questionnaire is the same PRO instrument and uses a 7 day recall period. The MPN-SAF TSS 2.0 will be translated and available on the eDiary device in several different languages to accommodate an international study.

In addition, the patient global impression assessment questionnaire (Appendix 11) will be completed at the end of Week 12, the end of Week 24 or the end of treatment visit, and every 3 months up to 2.5 years.

7.1.1.4 Other Assessments

Patients will be followed for leukemic transformation and frequency of RBC and platelet transfusions. DNA samples will also be collected for analysis of mutations associated with myelofibrosis at baseline and Week 24.

7.1.2 Safety

Safety assessments will be performed as described below until approval of Amendment 6, at which point assessments cease following the patient's End-of-Treatment, or 30-day post (EOT) visit as applicable.

7.1.2.1 Adverse Events

All AEs, including serious adverse events (SAEs), will be collected during the clinical study from the time the patient signs the informed consent through 30 days following last dose of study treatment. For screened patients who are not randomized, only SAEs occurring between the time of informed consent and determination of screen failure are to be reported; AEs occurring in this time period that do not meet the definition of an SAE do not need to be reported. SAEs that occur after study completion and are considered by the investigator to be related to pacritinib should be reported to the Sponsor.

7.1.2.2 Hematology

Hematology parameters including CBC, differential, platelet count, and hemoglobin A1C will be evaluated at screening, baseline, the end of week 4, the end of Week 12, the end of Week 24 or the end of treatment visit, every 3 months during the follow up period, and 30 days after the last dose of study treatment. In addition, for patients with baseline platelet count of $\leq 50,000/\mu$ L, the platelet count will be monitored weekly by the central laboratory for the first 8 weeks, then monthly if counts remain $\leq 50,000/\mu$ L. Samples collected at any visits for platelet counts must be submitted to the central laboratory for analysis, but in addition can be analyzed locally for assessment and management of patients in real time. Additional platelet count testing should be done as clinically indicated.

7.1.2.3 Coagulation Testing

Coagulation testing will include PT, INR, PTT, and TT at screening, baseline, the end of week 4, the end of Week 12, the end of Week 24 or the end of treatment visit, every 3 months during the follow up period, and 30 days after the last dose of study treatment. Additional coagulation testing should be done as clinically indicated.

These results will be taken into account, together with baseline platelet counts and prior medical history of bleeding, to help guide ongoing hematologic monitoring of platelet counts and clinical monitoring for bleeding.

7.1.2.4 Serum Chemistry

Screening laboratory assessments should be performed at least 1 week after the end of prior therapy. Serum chemistry parameters (ALT/SGPT and AST/SGOT, alkaline phosphatase, bilirubin [total, direct, and indirect], creatinine, lactate dehydrogenase (LDH), sodium, potassium, chloride, bicarbonate, calcium, phosphate, magnesium, blood urea nitrogen (BUN)/urea, albumin, amylase, lipase, glucose, cholesterol, uric acid, and high specificity CRP) will be evaluated by a central laboratory at screening, at baseline, and as clinically indicated. Unscheduled chemistry assessments may be performed locally and/or centrally whenever clinically indicated. Blood samples drawn at unscheduled visits for serum chemistry evaluation should be submitted to the central laboratory for assessment in addition to any local laboratories as needed for timely decisions regarding patient care.

7.1.2.5 ECG Assessment

All patients will have a 12-lead ECG (collected in triplicate)), including QTc calculation corrected by the Fredericia method, at screening, baseline, the end of Week 4, the end of Week 12, the end of Week 24 or the end of treatment visit, and every 3 months while in the follow-up period (pre-dose only for the post-24-week follow-up visit and 30 days after the last dose of study treatment. Additional ECGs may be required in the event patient demonstrates QTc prolongation. See Section 6.5.3 for appropriate pacritinib dose adjustment guidelines and additional ECG requirements. All ECGs will be centrally read by a blinded independent cardiologist.

7.1.2.6 Cardiac Ejection Fraction Assessment

All patients will have ejection fraction checked (echocardiogram or MUGA scan) at screening, the end of Week 4, the end of Week 12, the end of Week 24, or the end of treatment visit, and every 6 months while in the follow up period, and 30 days after the last dose of study treatment. If pacritinib treatment is resumed after holding for ejection fraction abnormality, ejection fraction should be reassessed about

14 days later, then at least every 3 months as per the above schedule. Additional ejection fraction testing shall be done as clinically indicated (see dosage modifications in Section 6.5).

The screening evaluations listed below are to be carried out **between 35 and 7 days prior to the start of treatment**, with the exception of MRI or CT scan, which must be performed between 10 and 4 days prior to the start of the study.

- Medical history
- Vital signs, including pulse, systolic and diastolic blood pressure, respiratory rate, temperature, and body weight
- Physical examination, including spleen measurement
- 12-lead ECG (collected in triplicate)
- Ejection fraction assessment (Echocardiogram or MUGA)
- ECOG performance status
- Hematology: CBC with differential, platelet count and hemoglobin A1C

- Coagulation testing including PT, INR, PTT, and TT
- Serum chemistry, including ALT/SGPT and AST/SGOT, alkaline phosphatase, bilirubin (total, direct, and indirect), creatinine, LDH, sodium, potassium, chloride, bicarbonate, calcium, phosphate, magnesium, BUN/urea, albumin, amylase, lipase, glucose, cholesterol, uric acid, and high specificity CRP
- Serum pregnancy test for women of childbearing potential (WOCBP). For WOCBP in the UK, the screening pregnancy test must occur no longer than 7 days before the first study drug administration. If fertile, males and females must agree to use effective birth control methods during the study. Women of childbearing potential must use highly effective methods (defined as those resulting in a failure rate of <1% per year when used consistently and correctly) for the duration of study treatment and for 12 months after last dose of study drug. The contraceptive methods considered highly effective are intrauterine devices and hormonal contraceptives (contraceptive pills, implants, transdermal patches, hormonal vaginal devices, or injections with prolonged release). Males must use a condom for the duration of the study and for 90 days after the last dose of study treatment. When abstinence is used as a method of birth control, only true abstinence is acceptable, when this is in line with the preferred and usual lifestyle of the patient. Periodic abstinence (calendar, ovulation, symptothermal, and post-ovulation methods) and withdrawal are not acceptable methods of contraception.

- MRI (preferred) or CT scan (without contrast) for measurement of spleen volume (to be performed between Days -10 and -4 prior to the start of treatment).
- Begin collecting patient-reported disease-related symptoms on MPN-SAF TSS 2.0 via electronic diary. Patient must complete daily for 7 consecutive days prior to starting treatment.
- Baseline symptoms and AEs
- Concomitant medications
- Transfusion history (RBC and platelets)

7.1.5 Randomization and Start of Week 1 (Baseline; -1 day)

Randomization: Patient must first sign informed consent, then complete all screening procedures, and meet all eligibility criteria.

- Vital signs, including pulse, systolic and diastolic blood pressure, respiratory rate, temperature, and body weight
- Physical examination, including height, clinical signs and symptoms, and spleen measurement
- 12-lead ECG (collected in triplicate)
- Hematology: CBC with differential, platelet count and hemoglobin A1C; patients with baseline platelet count of ≤ 50,000/µL, platelet count will be monitored weekly by the central laboratory for the first 8 weeks, then monthly if counts remain ≤ 50,000/µL. Blood samples drawn at unscheduled visits for the assessment of hematology parameters should be submitted to the central laboratory for assessment in addition to any local laboratories as needed for timely decisions regarding patient care. Additional hematology testing should be done as clinically indicated.
- Coagulation testing including PT, INR, PTT, and TT
- Serum chemistry, including ALT/SGPT and AST/SGOT, alkaline phosphatase, bilirubin (total, direct, and indirect), creatinine, LDH, sodium, potassium, chloride, bicarbonate, calcium, phosphate, magnesium, BUN/urea, albumin, amylase, lipase, glucose, cholesterol, uric acid, and high sensitivity CRP. Blood samples drawn at unscheduled visits for the assessment of serum chemistry parameters should be submitted to the central laboratory for assessment in addition to any local laboratories as needed for timely decisions regarding patient care.

- Continue collecting patient-reported disease-related symptoms on MPN-SAF TSS 2.0 via electronic diary daily
- For patients participating in dense PK sampling: PK sample at 2 hours (± 5 minutes), 4 hours (± 10 minutes), 6 hours (± 15 minutes), and 8 hours (± 15 minutes) postdose and 24 hours postdose (within 30 minutes before the Day 2 dose)
- PD sample within 30 minutes prior to 0 hours (predose)
- DNA sample
- Dispense pacritinib
- Begin pacritinib dosing
- Baseline symptoms and AEs
- Concomitant medications
- Transfusion history (RBC and platelets)
- Provide prescription for loperamide (Imodium®) or a similarly effective antidiarrheal drug

7.1.6 End of Week 4, Study Day 28 (± 3 days)

- Vital signs, including pulse, systolic and diastolic blood pressure, respiratory rate, temperature, and body weight
- Physical examination, including spleen measurement
- 12-lead ECG (collected in triplicate)
- Ejection fraction assessment (Echocardiogram or MUGA)
- ECOG performance status
- Hematology: CBC with differential, platelet count and hemoglobin A1C
- Coagulation testing including PT, INR, PTT, and TT
- Serum chemistry as clinically indicated
- Serum pregnancy test for women of childbearing potential within the United Kingdom
- Continue collecting patient-reported disease-related symptoms on MPN-SAF TSS 2.0 via electronic diary daily
- Dispense pacritinib
- Perform pacritinib accountability
- AEs
- Concomitant medications
- Transfusion history (RBC and platelets)

7.1.7 End of Week 12, Study Day 84 (± 7 days)

- Vital signs, including pulse, systolic and diastolic blood pressure, respiratory rate, temperature, and body weight
- Physical examination, including spleen measurement
- 12-lead ECG (collected in triplicate)
- Ejection fraction assessment (Echocardiogram or MUGA)
- ECOG performance status
- Hematology: CBC with differential, platelet count and hemoglobin A1C
- Coagulation testing including PT, INR, PTT, and TT

- Serum chemistry as clinically indicated
- Serum pregnancy test, if mandated by country-specific requirement
- MRI (preferred) or CT scan (without contrast) for measurement of spleen volume (for each patient, the same imaging modality should be used throughout the study)
- Continue collecting patient-reported disease-related symptoms on MPN-SAF TSS 2.0 via electronic diary daily
- Patient global impression assessment
- For all patients: PK samples at 30 minutes to 0 hours (predose), 4 hours (± 10 minutes), and 8 hours (±15 minutes) postdose
- For patients participating in dense PK sampling: 30 minutes to 0 hours (predose), 2 hours (± 5 minutes), 4 hours (± 10 minutes), 6 hours (± 15 minutes), and 8 hours (± 15 minutes) postdose
- PD sample within 30 minutes prior to 0 hours (predose)
- Dispense pacritinib
- Pacritinib accountability
- AEs
- Concomitant medications
- Transfusion history (RBC and platelets)

7.1.8 End of Week 24, Study Day 168 (± 7 days), or End of Treatment

- Vital signs, including pulse, systolic and diastolic blood pressure, respiratory rate, temperature, and body weight
- Physical examination, including spleen measurement
- 12-lead ECG (collected in triplicate)
- Ejection fraction assessment (Echocardiogram or MUGA)
- ECOG performance status
- Hematology: CBC with differential, platelet count, and hemoglobin A1C
- Coagulation testing including PT, INR, PTT, and TT
- Serum chemistry as clinically indicated
- Serum pregnancy test, if mandated as a country-specific requirement
- MRI (preferred) or CT scan (without contrast) for measurement of spleen volume (for each patient, the same imaging modality should be used throughout the study)
- Continue collecting patient-reported disease-related symptoms on MPN-SAF TSS 2.0 via electronic diary daily
- Patient global impression assessment
- For all patients: PK samples at 30 minutes to 0 hours (predose), 4 hours (±10 minutes), and 8 hours (±15 minutes) postdose
- For patients participating in dense PK sampling: 30 minutes to 0 hours (predose), 2 hours (± 5 minutes), 4 hours (± 10 minutes), 6 hours (± 15 minutes), and 8 hours (± 15 minutes) postdose
- PD sample within 30 minutes prior to 0 hours (predose) [collected at Week 24; not collected at End of Treatment]
- Dispense pacritinib (for patients continuing to receive treatment)
- Perform pacritinib accountability
- AEs

- Concomitant medications
- Transfusion history (RBC and platelets)
- DNA Sample [collected at Week 24; not collected at End of Treatment]

7.1.9 **30-Day Post End of Treatment (30 ±3 days After End of Treatment)**

For patients who transition to and continue treatment under an expanded access program, the 30-Day Post End of Treatment assessment will not be performed.

- 12-lead ECG (collected in triplicate)
- Ejection fraction assessment (Echocardiogram or MUGA)
- Hematology: CBC with differential, platelet count and hemoglobin A1C
- Coagulation testing including PT, INR, PTT, and TT
- Serum chemistry as clinically indicated
- Last time point for collection of patient-reported disease-related symptoms on MPN-SAF TSS 2.0 via electronic diary. Patient to return electronic diary device during visit.
- Last time point for collection and follow-up of nonserious AEs (related or not related) and SAEs deemed not related to study treatment or procedures.
- Concomitant medications

8 Pharmacokinetic and Pharmacodynamic Analysis

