¹ Screening procedures must be completed between Days -35 and -7, before treatment initiation, with the exception of the screening (baseline) MRI or CT scan, which must be parformed between Days -10 and -4								
² Day 1 assessments are required to be performed prior to initiation of study treatment and can be performed up to 24 hours prior to initiation of study treatment. At the baseline visit, all patients will be provided with a prescription (and instructions to fill that prescription) for loperamide (Imodium) or a similarly effective antidiarrheal drug. Patients will be instructed to start taking the prescribed loperamide or other antidiarrheal drug per package and physician instructions as soon as they notice any change in frequency or consistency of bowel movements after starting study treatment.								
³ The study visit at week 4 has a scheduling window of ±3 days; however, all procedures other than MRI or CT should be performed on the same day's visit within ±24 hours. ⁴ The study visits at weeks 12 and 24 have a scheduling window of ±7 days; however, all procedures other than MRI or CT should be performed on the same day's visit within ±24 hours.								

Table 1. PAC203 Study Assessments Calendar²⁰

- ⁵ The End of Treatment visit is scheduled within 7 days after terminating study treatment. A final visit to assess events is scheduled 30 ±3 days after the last dose of study treatment. If treatment ends at a regularly scheduled visit, these procedures may be performed at that time.
- ⁶ Informed consent must be obtained before any study-specific washout. This may require 2 weeks (A 2-week washout will be required for anticoagulation agents, antiplatelet agents (except aspirin doses of ≤ 100 mg/day), strong CYP3A4 inhibitors, strong CYP450 inducers, and QTc prolonging agents) or 28 days if patient was taking any experimental therapies. Patients not requiring washout may sign the Informed Consent Form at any time prior to screening procedures.
- ⁷ Vital signs include blood pressure, pulse, respiratory rate, temperature, and body weight.
- ⁸ Height should be measured only at baseline. Spleen size assessed by physical examination as the distance below the LCM at the midclavicular line.

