Patients who discontinue pacritinib treatment prior to Week 24, with or without disease progression, will continue to follow this Study Assessments Calendar through Week 24.

Patients who undergo splenic irradiation, splenectomy, or who initiate any non-protocol-directed anti-myelofibrosis treatment at any time must complete the *End of Treatment* visit within 7 days of stopping the drug and *30 Day Post End of Treatment* visit within 30 days of *End of Treatment* visit, but will not complete any additional visits.

If an arm is closed, patients randomized to that arm will end pacritinib treatment and complete the *End of Treatment* visit within 7 days of stopping the drug and *30 Day Post End of Treatment* visit within 30 days of *End of Treatment* visit.

Unscheduled visits should include physical examination, laboratory tests, and radiographic evaluations as clinically indicated in the judgement of the investigator and these results must be entered into the EDC.

Additional visits may be required for patients with baseline platelet count $\leq 50,000/\mu$ L as well as patients who have pacritinib dose modifications due to hematologic, cardiac, diarrhea, or other non-hematologic toxicities in addition to those specified in Section 6.5. Samples drawn for clinical laboratory assessments at unscheduled visits should be submitted to the central laboratory for analysis in addition to any local analysis that may be performed for the purpose of patient management. See Section 6.5 for details.

Abbreviations

Abbreviation	Full Term
AE	adverse event
ALT	alanine aminotransferase (syn: see SGPT)
ASCT	allogeneic stem cell transplantation
AST	aspartate aminotransferase (syn: see SGOT)
AUC	area under the curve
AUC _{inf}	area under the curve to infinite time
AUC _{0-t}	area of the curve up to the last measurable concentration
BAT	best available therapy
BID	twice per day
BUN	blood urea nitrogen
CBC	complete blood count
C _{max}	maximum concentration observed
C _{min}	minimum concentration observed
CRF(s)	case report form(s)
СТ	computed tomography
CTCAE	Common Terminology Criteria for Adverse Events
CYP450	cytochrome P450
DIPSS	Dynamic International Prognostic Scoring System
ECG	electrocardiogram
ECOG	Eastern Cooperative Oncology Group
eCRF	electronic case report form
EDC	electronic data capture
EPs	erythroid progenitors
ET	essential thrombocythemia
FAS	Full Analysis Set
FDA	Food and Drug Administration
FLT3	fms-like receptor tyrosine kinase 3

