10.2 Total Symptom Score (TSS)

The MPN-SAF TSS 2.0 is an instrument measuring disease impact among patients with Myelofibrosis (MF). Supportive measures of efficacy are the percent change from baseline in TSS as measured by the MPN-SAF TSS 2.0 and the proportion of patients with TSS reduction $\geq 50\%$ at Weeks 12 and 24. Patients will begin reporting symptoms via electronic diary at least 7 days before starting pacritinib treatment and will continue until the Week 48 visit. After Week 48, patients will complete a 7-day recall version of the symptom assessment at each study visit.

TSS Algorithm

- **The daily TSS** is the sum of the scores for the following symptoms: tiredness, early satiety, abdominal discomfort, night sweats, pruritus, bone pain, and pain under ribs on the left side (excludes the inactivity score).
- **The baseline TSS** is the mean of the daily TSS over the 7 consecutive days prior to the start of treatment. Missing values during these days are handled as described below (section 7.2.2).
- **Week 24 TSS** is the mean of the daily TSS obtained during the 28 consecutive days prior to the post-baseline spleen volume scan date (i.e. Week 12 or 24 visit date if scan date is

missing). A similar approach will be performed when defining the TSS values for Weeks 12, 36 and 48.

- The percent reduction in TSS from baseline to the Week 12 or 24 visit is computed by:

$$\text{TSS \% Reduction} = - \left(\frac{\text{Week 12 or 24 TSS} - \text{Baseline TSS}}{\text{Baseline TSS}} \right) * 100.$$

Handling of Missing TSS Values

- If any of the seven individual symptoms scores are missing, the TSS for that day will be considered as missing.
- The baseline TSS is set to missing if fewer than 4 daily TSS are available out of the 7 consecutive days prior to the start of study treatment.
- The Week 24 TSS is set to missing if fewer than 20 daily TSS are available out of the 28 consecutive days prior to Week 24 spleen volume scan date (or Week 24 visit date if scan date is missing). In sensitivity analyses where Week 24 TSS is derived from the mean of 7 consecutive days of daily TSS, the Week 24 TSS is set to missing if fewer than 4 daily TSS are available out of the 7 consecutive days prior to Week 24 spleen volume scan date (or Week 24 visit date if scan date is missing). Missing TSS at other post-baseline time-points is similarly handled. A similar approach will be performed when defining the TSS values for Weeks 12, 36 and 48.

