12 EFFICACY ENPOINTS AND ANALYSES

12.1 PRIMARY EFFICACY ENPOINTS

12.1 1 Spleen Volume Reduction

The primary efficacy variable for dosage selection is the percent reduction in spleen volume from baseline as measured by MRI or CT at Weeks 12 and 24..

Descriptive statistics of spleen volume at baseline, Week 12, Week 24, and at End of Treatment will be presented by treatment arm. Spleen volume at End of Treatment is defined as the spleen volume collected at the end of treatment visit or the last spleen volume measured on treatment if not measured at end of treatment. Descriptive statistics of percent reduction in spleen volume at Weeks 12 and 24 and at End of Treatment will be presented by treatment arm. These descriptive statistics include counts, mean, standard deviation, standard error of the mean, median, 25th percentile, 75th percentile, minimum, and maximum. As a supportive measure of efficacy, the counts and proportions of patients with spleen volume reduction (SVR) $\geq 35\%$ at Weeks 12 and 24 and at End of Treatment will be presented by treatment arm. The exact (Clopper-Pearson) 95% confidence intervals (CIs) for the proportions will also be presented. Additional supportive analyses include imputing missing Week 24 spleen volume with the previous post-baseline (Week 12) spleen volume, if any, and repeating the above analyses. These analyses will be repeated for spleen volume measured after Week 24 in long term follow up.

12.1 2 Total Symptom Score (TSS) Analysis

Descriptive statistics of individual symptoms and TSS at baseline, every 12 weeks, and at End of Treatment will be presented by treatment arm. Descriptive statistics of percent reduction in TSS every 12 weeks and at End of Treatment will be presented by treatment arm. The counts and proportions (including Clopper-Pearson 95% CIs) of patients with TSS reduction $\geq 50\%$ every 12 weeks and at End of Treatment will be presented by treatment arm. Supportive analyses include imputing missing Week 24 TSS with the previous post-baseline (Week 12) TSS, if any, and repeating the above analyses at Week 24.

As an anchor for patient-reported symptom assessment, the patient global impression assessment (PGIA) will also be summarized and evaluated for correlation with TSS. There is 1 domain in the PGIA instrument with possible scores ranging from 1 (very much improved) to 7 (very much worse).

12.1 3 Patient Global Impression Assessment

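### Protocol section 7.1.9 ends diary collection and takes back the device at the 30-day post-treatment visit, contradicting the text that keeps early stoppers on symptom scoring through Week 24

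*Protocol*

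**What the plan says.** **When the diary ends.** The checklist in Protocol section 7.1.9 (30-Day Post End of Treatment) makes that visit the final one for collecting "symptoms on MPN-SAF TSS 2.0 via electronic diary. Patient to return electronic diary device during visit". Its only exemption is for patients who move to expanded access.

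Section 7.1.1.3 says something different. Diary reporting starts "at least 7 days before starting pacritinib treatment and will continue until the Week 48 visit". Table 1 footnote 14 and SAP section 10.2 also run the daily diary to Week 48. Table 1 has no TSS mark in the 30-day column.

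**What early stoppers must do.** The Special Cases text after Table 1 says that patients who stop pacritinib before Week 24, with or without progression, "will continue to follow this Study Assessments Calendar through Week 24". Sections 3 and 3.3 say the same, and Table 1 marks the MPN-SAF TSS 2.0 at Weeks 12 and 24. Patients are released from this if they withdraw consent, die, have splenectomy or splenic irradiation, or start other anti-myelofibrosis treatment.

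**How the score is built.** SAP section 10.2 averages the daily scores over the 28 days before the scan: "The Week 24 TSS is set to missing if fewer than 20 daily TSS are available out of the 28 consecutive days". Other post-baseline time points are handled in the same way. SAP section 12.1.2 adds: "Supportive analyses include imputing missing Week 24 TSS with the previous post-baseline (Week 12) TSS, if any".

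**The concern.** A patient who stops early reaches the 30-day visit before Week 24, often by many weeks. Handing in the device there removes the only source of daily scores. The 7-day-recall paper form begins only at Week 48, so nothing replaces the diary.

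TSS is named in secondary objective 1 as a dose-response measure, and diary days that were never recorded cannot be recovered at analysis. The loss would fall only on patients who stopped treatment. One group is easy to identify. The only scheduled post-baseline scan before Week 24 is at Week 12, and section 3.3 ends treatment when spleen volume has grown by 25% or more while still asking for all assessments through Week 24. A patient who stops shortly after that scan would have a Week 24 spleen volume but no Week 24 TSS, so the two efficacy summaries would describe different patients.

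**Working it through.** The documents give no cut-off week, so this is calendar arithmetic. No missed diary entries are assumed, which favours the plan.

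**Inputs**
- Week 24 scan on Day 168 (Table 1), so the 28-day TSS window is Days 140 to 167 (SAP 10.2).
- Minimum of 20 daily scores (SAP 10.2).
- End of Treatment visit within 7 days of stopping (Table 1 footnote 5).
- 30-day visit: section 7.1.9 heads it "30 ±3 days After End of Treatment", while Table 1 footnote 5 says "A final visit to assess events is scheduled 30 ±3 days after the last dose of study treatment". The gap *g* from last dose to device return is therefore 27 to 33 days on the footnote, and up to 7 + 33 = 40 days on 7.1.9. The Special Cases text has a third version (within 30 days of the End of Treatment visit), which allows shorter gaps and would move the cut later.

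**Week 24 cut.** The 20th day of the window is 140 + 19 = Day 159. Not counting an entry on the return day itself, the device can go back on Day 160 at the earliest, so the last dose must be on Day 160 − *g* or later:
- *g* = 27: Day 133 (Week 19.0)
- *g* = 30: Day 130 (Week 18.6)
- *g* = 37: Day 123 (Week 17.6)
- *g* = 40: Day 120 (Week 17.1)

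Counting an entry on the return day moves each cut one day earlier. At *g* = 30 the latest failing last dose is then Day 128 instead of Day 129.

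**Diary days available out of 28, Day 168 scan** (last dose day + *g* − 140, bounded by 0 and 28):

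| Last dose | g = 27 | g = 30 | g = 37 | g = 40 |
|---|---|---|---|---|
| Week 14 (Day 98) | 0 | 0 | 0 | 0 |
| Week 16 (Day 112) | 0 | 2 | 9 | 12 |
| Week 17 (Day 119) | 6 | 9 | 16 | 19 |
| Week 18 (Day 126) | 13 | 16 | 23 | 26 |
| Week 19 (Day 133) | 20 | 23 | 28 | 28 |

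**Other scan days.** Within the ±7-day visit window (Days 161 to 175) the cut runs from Week 16.1 to Week 20.0. Across the SAP analysis window (Days 147 to 189) it runs from Week 14.1 to Week 22.0.

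**Sensitivity score, 4 of 7 days.** The window is Days 161 to 167 and the fourth day is Day 164, so return is on Day 165 or later. The last dose must be on Day 138 (*g* = 27) to Day 125 (*g* = 40) or later, that is Weeks 19.7 to 17.9. This does not rescue the score.

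**Week 12.** For a Day 84 scan the window is Days 56 to 83 and the 20th day is Day 75. At *g* = 30 the score fails for a last dose on Day 45 or earlier, or Day 44 or earlier if an entry on the return day counts.

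**The case against.** The strongest reply is that 7.1.9 is one bullet against several passages. The diary runs to Week 48 in three places, the text written specifically for early stoppers keeps them on the calendar, and the Week 24 checklist says to continue the daily diary. Table 1 treats the 30-day visit as the end of study, so 7.1.9 may have been written for patients for whom it really is the last visit. This stands in part. A reader might infer that early stoppers simply cannot supply the Week 24 score. The documents do not support that, because a site following the other passages would collect it. What remains is a contradiction, and the instruction on the wrong side of it is the one that physically removes the device.

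Amendment 6 complicates matters. Table 1 footnote 20 and section 7.1.1 say assessments cease after the End of Treatment or 30-day visit, as applicable. That could be read as supporting 7.1.9. However, the amendment ends treatment for patients at and beyond Week 24, and the Week 24 duty for early stoppers is still in the text.

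Two further inferences go too far:
- *A count per arm.* If one assumed that 10% to 30% stop before Week 18, 5 to 15 of 50 patients would lose the score. The documents give no such rate for this trial, and the figure includes patients released from visits, whose scores would be lost anyway.
- *That the loss flatters an arm with many early stops.* SAP 10.1 and 10.4 divide spleen responders by the full analysis set, but 10.2 states no denominator for TSS responders. If a missing score counts as non-response, such an arm is penalised instead. Several toxicity rules discontinue at 100 mg QD where higher levels step down, but that does not establish how stopping will differ by arm.

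It is also true that SAP 12.1.2 summarises TSS at End of Treatment, where early stoppers can contribute. That is not a Week 24 value. Nor is the Week 12 carry-forward, which is supportive only and reflects on-drug symptoms for anyone who stopped after Week 12.

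**Conclusion.** The contradiction is real. Where a site applies 7.1.9, a patient who stops before about Week 18 and is not released from visits will have a missing Week 24 TSS even with perfect diary compliance. This rests on a Day 168 scan and visit gaps of 27 to 40 days, which place the cut at Weeks 17 to 19. The Week 12 score is lost in the same way for a last dose at about Day 44 or earlier. The observed Week 24 TSS would then mainly describe patients who stayed on drug.

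The number of patients affected and the direction of any bias between arms cannot be determined from the documents. Severity is moderate: TSS is supportive, no hypothesis is tested, and the primary efficacy variable, spleen volume change, keeps its Week 24 scan.

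**What to change.** Replace the diary bullet in 7.1.9 with wording to this effect: patients who stop pacritinib before Week 24 and remain in follow-up keep the electronic diary, complete it daily through the Week 24 visit and return it then. The device comes back at the 30-day visit only if that visit falls at or after Week 24, or if the patient meets a Special Cases criterion that ends visits.

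Reconcile this sentence with the Amendment 6 text in Table 1 footnote 20 and section 7.1.1, so that it is clear whether an early stopper who has not reached Week 24 at approval still owes the Week 24 assessments.

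With the diary kept, all 28 days before the Week 24 scan can be recorded whatever the stop date, so the 20-day minimum can be met. The cost is one protocol sentence, the reconciliation and a notice to sites. Some devices stay with off-treatment patients a few months longer. No visits are added, since the Week 12 and Week 24 visits are already required.
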